9.6 Criteria to be Evaluable for Efficacy and Safety

A subject is evaluable for efficacy (reduction in mucositis) if at least 70% of the study mouth rinse doses were taken as documented on the daily log (Appendix A). Differences between groups in terms of response rate will be evaluated by ANOVA (section 8).

A subject is evaluable for safety (toxicity) if a minimum of one dose of the study mouth rinse was taken.

10. Correlative Studies (Laboratory Studies)

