2. Objectives/Endpoints

The primary objective of this Phase I/II study is to determine the maximum tolerated dose (MTD) of oral curcumin in patients who have chemotherapy-induced mucositis. The secondary objectives of this study are to determine whether oral curcumin:

- Decreases an objective measurement of oral mucositis
- Decreases the pain associated with oral mucositis
- Decreases the duration of mucositis
- Has an acceptable safety profile.

3. Study Design

This is a phase I/II study involving 2 parts: a dose escalation part and an expansion at the maximum tolerated dose.

In the first part, there will be 3 subjects at each dose level of curcumin (see table below). The doses will be taken 3 times each day for 14 days. Each dose will be taken as a mouth rinse containing curcumin and water, 3 times each day for 14 days. The mouth rinse will be used for 30 seconds and then swallowed. Subjects will be evaluated for dose-limiting toxicity (DLT, defined in section 6.1). The maximum tolerated dose (MTD, defined in section 2) will be determined. Subjects may participate in the study at a higher dose level, after they have completed the study at the current dose level and if they are eligible.

# Subjects	Curcumin/dose (gram)	Curcumin/day (gram)
3	0.33	1
3	1.0	3
3	2.0	6
3	3.0	9

In the second part of the study, there will be 23 subjects enrolled to an experimental (curcumin) arm and 23 subjects enrolled to a control (standard of care) arm. Subjects will be randomized to take a mouth rinse with or without the MTD of curcumin, 3 times each day for 14 days. The rinses will be swallowed. Subjects will be evaluated for response and toxicity. Subjects in the first part of the study may participate in the second part of the study, if they are eligible.

In both parts of the study, if the mucositis score \leq Grade 2 but is unresolved after 14 days of taking the study mouth rinse (curcumin or control), then the subject will

continue to receive the study mouth rinse until the mucositis is resolved (Grade 0).

This study will involve 12 subjects in the first part, plus an additional 3 subjects if a dose-limiting toxicity occurs (see section 2) and 46 subjects in the second part for a total of 61 subjects. This study is expected to take 2 years to complete enrollment, treatment and follow-up (6 months for the first part and 18 months for the second part).

4. Subject Selection

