4.2 Exclusion Criteria

- Current use of therapeutic doses of anticoagulants such as warfarin or antiplatelet agents (prophylactic doses and agents are acceptable)
- Biliary tract obstruction or cholelithiasis
- History of gastric or duodenal ulcers or hyperacidity syndromes
- AST or ALT $>$ 2 x ULN
- Total bilirubin \geq 2 x ULN
- INR $>$ 1.5
- Previous stem cell transplant (allogeneic or autologous)
- Preexisting oral disease, such as active oral infection, trauma to the oral mucosa or oral ulceration prior to chemotherapy
- Known allergy/hypersensitivity to curcumin, yellow food colorings, or other members of the Zingiberaceae (ginger) family
- Pregnant or breastfeeding

Potential subjects are identified by medical record review. Eligible subjects are asked to give their written consent to participate in this study. The tests required to screen subjects for this study include a pregnancy test, INR and CMP.

5. Study Procedures and Schedule

The study mouth rinse will be initiated when subjects have $>$ grade 2 mucositis, which could be at any point during their chemotherapy cycle. Subjects who develop $>$ grade 2 mucositis will receive appropriate adjustments in their chemotherapy dose to reduce toxicity with subsequent cycles.

In the first part, there will be 3 subjects at each dose level of curcumin. Each dose will be given as a mouth rinse containing curcumin and water.

In the second part, subjects will be randomized to take a mouth rinse with the MTD of curcumin or a standard mouth rinse, 3 times each day for 14 days. The curcumin mouth rinse will be designated “study mouth rinse” to differentiate it from the standard mouth rinse.

All subjects will be instructed to rinse their mouths with the study or standard mouth rinse 3 times each day for 14 days. Subjects will be instructed to use the study or standard mouth rinse for 30 seconds and then swallow the rinse. Subjects will be instructed not to eat within one hour after using the study or standard mouth rinse. Subjects will be instructed to use a saline mouth rinse after eating any food to keep their mouth clean. A daily log (Appendix A) will be available for each subject and will include a checklist that will simplify the rinsing schedule as well as an area for the subject (or family member) to document mouth rinse administration. No other adjunctive topical treatment will be used during the study.

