This visit will occur 7 days (+/- 1 day) after Visit 2. A mucositis assessment (CTAE version 4.0 and WHO Oral Toxicity Scale) will be conducted and documented by a health provider (Appendix B), who will also review and follow up on any side-effects that the subject is experiencing and check the daily log (Appendix A) to ensure that the subject is complying with the study. Sufficient mouth rinse will be given to the subject for the second week of the study. A blood sample will be obtained to assess liver function (CMP) and clotting function (PT and INR). A blood and saliva sample will be obtained for research purposes (section 10). This visit will take approximately 30 minutes.

5.1.5 Phone call 2

On day 10 or 11 after the first day of taking the mouth rinse for the study, the subject will be called by a study staff member, who will review and follow up on any side-effects that the subject is experiencing and answer any questions about the study or study mouth rinse. The staff member will remind the subject to complete a subject self-assessment tool (Appendix C) and the daily log (Appendix A) and bring them to the next visit. The phone call will take about 15 minutes.

5.1.6 Visit 4

This visit will occur 7 days (+/- 1 day) after Visit 3. A mucositis assessment (CTAE version 4.0 and WHO Oral Toxicity Scale) will be conducted and documented by a health provider (Appendix B), who will review and follow up on any side-effects that the subject is experiencing and obtain the daily log (Appendix A) from the subject. A blood sample will be obtained to assess liver function (CMP) and clotting function (PT and INR). A blood and saliva sample will be obtained for research purposes (section 10). If the mucositis score \leq Grade 2 but is unresolved, then the subject will continue to receive the study mouth rinse (curcumin or standard mouth rinse) until the mucositis is resolved (Grade 0). Sufficient mouth rinse will be given to the subject for the subsequent week of the study. This visit will take approximately 30 minutes.

5.1.7 Phone call 3

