5.2 Study Calendar

Study Procedure	Visit 1 (Screening)	Week 1		Week 2		Week 3		Week 4- mucositis resolution		Final visit
	day -1	Visit 2: day 0	Phone call 1: day 3	Visit 3: day 7	Phone call 2: day 10	Visit 4: day 14	Phone call 3: day 17	Visit: For phase II: weekly cycle repeated until mucositis is resolved (and no AEs)	Phone calls	
activity window		At or w/in 48hr of Visit 1	+ 1 day	+/- 1 day	+ 1 day	+/- 1 day	+ 1 day	+/- 1 day	+ 1 day	+/- 1 day
Sign Informed Consent	X									
Oral exam for hygiene	X									
Pregnancy test	X ¹									
Provider mucositis assessment ²	X	X ³		X		X		X ^a		X
Provider supplies study mouth rinse		X		X		X ^a		X ^a		X
Provider supplies study journal, self-assessment		X		X		X ^a		X ^a		X
Provider collects journal and self-assessments				X		X		X ^a		X
Remind subject to complete self-assessment		X	X		X		X		X ^a	
Blood collection for liver function (CMP) ⁴	X			X		X		X ^a		X
Blood collection for clotting (PT and INR) ⁴	X			X		X		X ^a		X
Research blood collection ⁵		X		X		X		X ^a		
Research saliva collection ⁵		X		X		X		X ^a		
Collect AEs			X	X	X	X	X	X ^a	X ^a	X
Review of concomitant medications	X	X		X		X		X ^a		X

¹ Blood or urine pregnancy test, if not already done as part of standard of care

² Includes CTAE version 4.0 and WHO oral Toxicity scale.

³ Mucositis assessment at Visit 2, only if a different day than Visit 1 (does not need to be repeated if Visit 1 and 2 are done on the same day)

⁴ Does not need to be repeated if already done for standard of care.

⁵ 6 ml of peripheral blood into a non-anti-coagulated tube, 2 ml saliva into a sterile tube; processed and stored as described in the operations manual.

^a Only if subject is still taking study mouth rinse based on improvement of mucositis at each visit, beginning at visit 4.

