6.2 Criteria for Subject Removal

A subject will be removed from the study for the following reasons:

- Dose limiting toxicity.
- No improvement in mucositis after 14 days of taking the study mouth rinse.
- Patient decision to withdraw consent or discontinue the study.
- Deemed by the physician to be the best medical interest of the patient.
- At the discretion of the investigator, patients who are non-compliant.

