This study will involve 12 subjects in the first part, plus an additional 3 subjects if a dose-limiting toxicity occurs (see section 2). This sample size is similar to other phase I dose escalation studies and will result in a determination of maximum-tolerated dose. The first objective for the second part (n=46) is to determine whether curcumin decreases an objective measurement of oral mucositis. Mucositis assessment will be conducted by the provider using the WHO scale and CTCAE scale. The scales are continuous between 0 and 4. Analysis of variance will be used to compare the two groups of subjects (standard mouth rinse versus study mouth rinse) separately for each time period (baseline and each week after study mouth rinse initiation). In a one-way ANOVA study, sample sizes of 23, and 23 are obtained from the 2 groups whose means are to be compared. The total sample of 46 subjects achieves 91% power to detect differences among the means versus the alternative of equal means using an F test with a 0.05 significance level. The size of the variation in the means is represented by their standard deviation which is 0.50. The common standard deviation within a group is assumed to be 1.00.

9. Measurement of Effect

Differences between the two mouth rinse groups will be studied with the chi-square test for categorical factors and the analysis of variance F-test for continuous variables with a 0.05 significance level.

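### Section 9.6 restricts the randomised efficacy comparison to subjects who logged at least 70% of doses, while section 8 powers it on all 46, and no all-randomised analysis is named

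*Combined protocol and SAP*

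**What the plan says.** Section 9.6 sets the efficacy population: "A subject is evaluable for efficacy (reduction in mucositis) if at least 70% of the study mouth rinse doses were taken", judged from the daily log. Its next sentence reads "Differences between groups in terms of response rate will be evaluated by ANOVA (section 8"). The only other population in that section is for safety, which needs one dose.

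Section 8 describes the ANOVA: the two rinse groups are compared on provider-assessed WHO and CTCAE scores at baseline and each week. It states that "The total sample of 46 subjects achieves 91% power to detect differences among the means" at the 0.05 level. The Precis and section 3 show that 46 is the number enrolled and randomised, 23 per arm. Section 8 states no adherence filter and no allowance for non-evaluable subjects.

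Section 6.2 opens "A subject will be removed from the study for the following reasons" and lists, among others, dose-limiting toxicity, physician judgement and non-compliance. In the section 5.2 calendar, the Visit 3 and Visit 4 provider mucositis assessments carry no condition. From week 4 they carry the note "Only if subject is still taking study mouth rinse based on improvement of mucositis at each visit, beginning at visit 4".

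The supplied text names no all-randomised or sensitivity population for efficacy and no method for missing assessments.

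**The concern.** Randomisation makes the two arms comparable at entry. A filter on logged doses acts afterwards, on something the assigned rinse can itself influence. Differential adherence is plausible here. One rinse is a Benadryl, Maalox and lidocaine mixture prepared by the pharmacy (section 5.3). The other is a curcumin powder that subjects mix with water at home (section 5.4). Section 6 lists nausea, vomiting and GI distress as possible effects of curcumin. If one arm loses more subjects who are faring badly, the subjects kept in that arm look better than the arm as randomised.

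Efficacy is a secondary objective of the study, but section 8 calls it the first objective of the second part, and 46 of the 61 planned subjects are enrolled for it. It is the only comparison with a power statement. With the plan as written, a positive or negative result from the 70% set would have no pre-specified all-randomised result beside it.

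**Working it through.** **Inputs from the documents.** 23 subjects per arm; SD of the two group means 0.50; within-group SD 1.00; F test at 0.05 (section 8). Three rinses a day for 14 days (section 5). The 70% threshold (section 9.6).

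**Inputs that are assumptions.** The documents give no exclusion rate and no difference in grade between excluded and kept subjects. The values below are illustrative.

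**1. Reproduce the 91%.** For two groups, an SD of means of 0.50 is a mean difference of 1.0. The noncentrality is 46 × 0.50² / 1.00² = 11.5, with 1 and 44 degrees of freedom. Power is 91.25%, so the stated figure is correct when all 23 + 23 enter the test.

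**2. Power if the filter removes subjects equally and the effect is unchanged.**

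| Analysed per arm | Power |
|---|---|
| 23 | 91.2% |
| 22 | 90.0% |
| 20 | 86.9% |
| 18 | 83.0% |

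**3. Who fails the filter.** Section 9.6 does not define the denominator. If it is the planned 3 × 14 = 42 doses, 70% is 29.4, so 30 logged doses pass and 29 fail. Thirty doses are 10 full days. A subject who stops or is removed before completing day 10 is therefore excluded.

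**4. Bias with no true effect.** Higher scores are worse. Let p be the fraction of an arm excluded and g the mean grade of excluded minus kept subjects. The kept mean is the full-arm mean minus p × g. The spurious advantage to curcumin is (p for curcumin − p for control) × g.

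With 5 of 23 curcumin and 2 of 23 control excluded, the analysis has 18 v 21 subjects (37 degrees of freedom, critical t 2.026). The shift is (3/23) × g. Noncentrality is shift × √(18 × 21 / 39) = shift × 3.113.

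| g | Shift | Noncentrality | False result favouring curcumin | False result favouring control | Total |
|---|---|---|---|---|---|
| 0.5 | 0.0652 | 0.203 | 3.9% | 1.55% | about 5.5% |
| 1.0 | 0.1304 | 0.406 | 5.9% | 0.92% | 6.8% |

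The nominal values are 2.5% per side and 5% in total.

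**5. Direction.** With 2 curcumin and 5 control excluded, the false rate favouring curcumin falls to 1.55% (g = 0.5) or 0.92% (g = 1). Changing the sign of g has the same reversing effect, for example if subjects who heal early skip doses. With 5 excluded from each arm and equal g the shift is 0 and each side stays at 2.5%.

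**6. Under a true 1-grade effect.** With 2 curcumin and 5 control excluded, power is 85.8% from the smaller numbers alone. The observed difference also shrinks to 1 − (3/23) × g, which is 0.935 or 0.870, and power becomes 80.9% or 75.1%.

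**7. Cost of analysing everyone.** If an assumed 10% or 20% of curcumin subjects gain nothing, the mean difference is 0.9 or 0.8. Power with 23 v 23 is then 84.7% or 75.6%.

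**The case against.** The strongest reply is that section 8 stands alone. It describes weekly score comparisons on 46 subjects with no filter, whereas 9.6 speaks of a response rate. One could read section 8 as already covering everyone, with the filter governing response only. That reading is available and the text is not fully clear. But 9.6 sends its comparison to the section 8 ANOVA by name, and section 8 defines no response rate. The cross-reference favours treating the two as one comparison, and the endpoint mismatch itself needs correcting.

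A second reply is that evaluable sets have a legitimate use in a small phase II part, and that analysing everyone dilutes the effect. Both are true. At 20% dilution the all-randomised power of 75.6% is below the 83.0% of a filtered set of 18 per arm. That 83.0%, however, assumes that filtering leaves the treatment difference undistorted, which is the point in doubt. Independent assessors (section 9.1) do not help, because the problem is who is analysed, not how they are graded.

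Three stronger readings are tempting and not supported.

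- **That the filter applies to curcumin subjects only.** Section 5 says "The curcumin mouth rinse will be designated “study mouth rinse” to differentiate it from the standard mouth rinse". Taken literally in 9.6, however, this would leave no control evaluable for efficacy or safety, and so no comparison. Section 3 uses the term for both arms ("after 14 days of taking the study mouth rinse (curcumin or control"), as does Visit 4 ("the subject will continue to receive the study mouth rinse (curcumin or standard mouth rinse) until the mucositis is resolved (Grade 0"). This is loose terminology.
- **That the lack-of-activity rule (6.3), pain (9.3) and duration (9.4) contradict 9.6** because they repeat no filter. A general evaluability rule need not be repeated, and silence is not contradiction.
- **That the 91% is miscalculated.** It reproduces.

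**Conclusion.** The point holds. As written, 9.6 selects the efficacy comparison on a post-randomisation variable, and the supplied text names no all-randomised analysis against which to check the result. The direction and size of any bias are unknown. In the 5 v 2 illustration the inflation is moderate: 3.9% to 5.9% against 2.5% on the side favouring curcumin, and about 5.5% to 6.8% against 5% overall. Those figures rest entirely on the assumed exclusion counts and on excluded subjects being 0.5 to 1 grade worse. The loss of power from smaller numbers is modest and is not the main issue.

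This should be fixed. It does not threaten the primary objective, which is the MTD. The remaining uncertainty is textual: section 8 states no filter, and 9.6 names a different kind of endpoint.

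**What to change.** 1. In sections 8 and 9.6, make the main Part 2 efficacy analysis all randomised subjects in their assigned arm, using the planned tests.
2. Keep the 70% set as a sensitivity analysis, worded as doses of the assigned rinse in both arms. Report exclusions with reasons by arm.
3. State that subjects who stop the rinse or are removed are still asked to attend the Visit 3 and Visit 4 provider mucositis assessments unless they withdraw consent. This changes what removal from the study means for follow-up only; no treatment rule changes.
4. State in section 8 that the 91% assumes all 46 are analysed and a full 1-grade difference.
5. Reconcile the response rate in 9.6 with the mean-score comparison in section 8.

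The cost is wording in sections 6.2, 8 and 9.6, a calendar note, and some effort to follow subjects who would otherwise leave. No new visit types are needed. The statistical price is possible dilution, as in step 7 of the working.

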10.1 Sample collection

- **Serum:** A sample (6 ml) of peripheral blood will be obtained by venipuncture into a non-anti-coagulated tube at each visit during administration of study mouth rinse. The sample will be kept at room temperature for 1 h and then centrifuged at 300 g for 10 minutes at 4°C, and the serum fraction will be divided into four aliquots that will be stored at -70°C until processed.
- **Saliva:** A sample (2 ml) of non-stimulated saliva will be collected into a sterile tube at each visit during administration of study mouth rinse and then taken into the laboratory on ice. The sample will be centrifuged at 300 g for 15 minutes at 4°C. The supernatant will be divided into 2 aliquots that will be stored at -70°C until processed.

10.2 Evaluation of Proinflammatory Cytokines

NF- κ B is among the most important and thoroughly studied transcription factors with regard to the development of mucositis. It is an important regulator of proinflammatory cytokines, such as TNF- α , IL-1 β , and IL-6. These proteins are effective mediators of injury, and the increase in the levels in tissue and peripheral blood correlates well with non-haematological toxicities induced by chemotherapy[17]. Levels of proinflammatory cytokines such as TNF- α , IL-1 β , and IL-6 will be evaluated in serum and/or saliva samples using a Becton

Dickinson Cytometric Bead Array (CBA) flow cytometric assay. This testing is required for participation in the study.

10.3 Future Research and Sample Disposition

Serum and saliva samples will be stored at -70°C in the Immunology Research Laboratory on the Aurora St. Luke's Medical Center campus. Samples will be coded. All patient identifiers will be removed. A key for the code will be stored in the office of the study staff. Only study staff will have access to the code. Samples that are left-over after the proinflammatory cytokine analysis will be stored at -70°C for future research on chemotherapy-induced mucositis. Subjects will be asked to complete a separate consent form for this future research. Samples will be stored until they are used up. If other researchers use the samples on an IRB-approved study, they will not be given any information that will link subject identifiers to the sample. If subjects do not consent to this future research, their leftover samples will be discarded following institutional procedures.

11. Data Collection

Data collected will include: patient demographic data, cancer treatment information (chemotherapy regimen, date started chemo), the name of the referring oncologist, dental work within the past six months and/or pre-existing mouth issues, medications within 30 days of screening, grade of oral mucositis prior to study and during the whole course of the study, pain scale, duration of mucositis, duration of neutropenia, the need and length of hospitalization, use and dosage of pain medicine, need for total potential nutrition, blood culture positive infection, other mucositis related complications and cytokine levels in blood and saliva.

If data from this study is published or otherwise shared with outside institutions, all identifying information will be removed and the data will be coded. The local study staff will have access to the code. There will be no differences in data collection between the different sites at Aurora Health Care that may eventually participate in this study.

12. Monitoring Plan

Careful evaluation to ascertain the toxicity and efficacy of topical curcumin on mucositis will be performed by the Principal Investigator and the research team. For all patients, the Principal Investigator will review all serious adverse events and will monitor the data and toxicities to identify trends weekly during the study. The Principal Investigator will be responsible for revising the protocol as needed to maintain safety. The IRB will review submitted adverse events to also evaluate trends and will require a follow up plan from the Principal Investigator whenever a trend is identified. Independent quality, compliance and safety monitoring of the study will occur at least once each year that the study is enrolling subjects and may include a review of protocol compliance, informed

consent documentation, data collection accuracy, adverse event reporting, patient safety and outcomes analysis.

13. Reporting Requirements

- Subject data accrued on this study will be reported in accordance with 21CFR 312.32.
- This study will utilize the CTCAE Version 4.0 for Adverse Event (AE) Reporting. The CTCAE v4.0 can be downloaded from the CTEP home page (<http://ctep.info.nih.gov>).
- The Principal Investigator will notify the IRB, and the FDA and other regulatory agencies of all serious adverse events as required by law or regulation.
- Reporting requirements to the Aurora IRB is described in IRB SOP RR:403 Ongoing Oversight of Approved Research and Reporting of Problems/Events.
- Reporting requirements to the FDA is described in the “Guidance for Industry and Investigators Safety Reporting Requirements for INDs and BA/BE Studies” December 2012:
<http://www.fda.gov/downloads/Drugs/GuidanceComplianceRegulatoryInformation/Guidances/UCM227351.pdf>.
- All participating investigators will be notified of IND Safety Reports by email.

